## 5.2. Determination of Sample Size

It is estimated that approximately 750 patients will enter the long-term extension study (RHBY) after completion of Studies RHBV, RHBW, or RHBX. This sample size is estimated based on the 1-year retention rates from ixekizumab psoriasis studies and from 1 secukinumab radiographic (rad)-axSpA study (Baeten et al. 2015), which had a retention rate of approximately 85%. It is anticipated that approximately 30% of the 750 patients will meet the entry criteria for randomized-withdrawal (Sieper et al. 2015). Approximately 100 patients who achieved a state of sustained remission on IXE80Q4W will be randomized in a 2:1 ratio to IXE80Q4W or placebo, and approximately 100 patients who achieved a state of sustained remission on IXE80Q2W will be randomized in a 2:1 ratio to IXE80Q2W or placebo in the double-blind RWR period. This total sample size of 200 will provide over 99% power to detect a difference in the proportion of patients who do not experience a flare between the Combined Ixekizumab treatment group (including Q2W and Q4W) and placebo using a 2-sided Fisher's exact test at the 0.05 level, assuming the flare rates are 10% for ixekizumab and 70% for placebo. Sample size and power calculations are calculated using nQuery+nTerim 3.0.

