**Table RHBY.6.1. Treatment Groups and Major Patient Populations for Analysis Periods for Study RHBY**

Population	Period	Analyses	Treatment Groups	Group Comparisons
Lead-In Period Safety Population	Combined Periods 1 & 2 Combined Periods 1, 2, & 3	Safety	IXE80Q2W IXE80Q4W Total IXE	Descriptive No inferential statistics
Long-Term Ixekizumab Treatment Efficacy Population	Combined Periods 1 & 2 Combined Periods 1, 2, & 3	Efficacy and health outcomes	IXE80Q2W a IXE80Q4W a Total IXE	Descriptive No inferential statistics
RW Safety Population	Period 2 Period 3	Safety	IXE80Q2W IXE80Q4W Total IXE Placebo	Total IXE vs. Placebo IXE80Q2W vs. Placebo IXE80Q4W vs. Placebo
RW ITT Population	Period 2 Combined Periods 2 & 3	Efficacy and health outcomes	IXE80Q2W IXE80Q4W Total IXE Placebo	Total IXE vs. Placebo IXE80Q2W vs. Placebo IXE80Q4W vs. Placebo
Ixekizumab Structure Population	At Week 56 for a 2-year assessment	Efficacy	IXE80Q2W IXE80Q4W Total IXE	Descriptive No inferential statistics
Flare Population with retreatment	Period 2, Combined Periods 2 and 3	Efficacy	PBO/IXE80Q2W PBO/IXE80Q4W PBO/IXE IXE80Q2W/IXE80Q2W IXE80Q4W/IXE80Q4W IXE/IXE	Descriptive No inferential statistics
Dose Escalation Population	Period 3	Efficacy	PBO/IXE80Q4W, IXE80Q4W/ IXE80Q4W Total	Descriptive No inferential statistics
Follow-Up Population	Period 4	Safety	IXE80Q2W IXE80Q4W Total IXE Placebo	Descriptive No inferential statistics

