- For AEs that are ongoing at the date of Visit in Week 104 or ETV, the maximum severity recorded for each LLT on or prior to the date of the Visit at Week 104 or ETV will be used as the follow-up baseline severity for that LLT.

If a partial or completely missing AE start date/time or end date/time is present, the following imputation rules will be utilized in the analysis:

- For the start date:
  - If year, month, and day are missing, then use the earlier of the patient's first visit date or the consent date.
  - If either month or month and day are missing, then use January 1.
  - If only day is missing, impute the first day of the month.
- For the start time:
  - Impose as 23:59
- For the end date:
  - If year, month, and day are missing, then use the patient's last visit date in the follow-up period.
  - If either month or month and day are missing, then use December 31.
  - If only day is missing, then use the last day of the month.
  - The imputed date will not be beyond the patient's last visit date in the follow-up period.
- For the end time:
  - Impose as 23:59.

- If there is any doubt, the event will be flagged as treatment-emergent or follow-up emergent according to the corresponding study period. If a follow-up emergent event is already counted as treatment-emergent during the prior treatment period, it will not be counted as a follow-up emergent event.

Adverse events and TEAEs will be summarized for the following study periods by treatment groups (see [Table RHBY.6.1](#)) and analysis populations, treatment comparisons between treatment groups in Period 2 will be conducted using a Fisher's exact test:

- Combined Periods 1 and 2, Combined Periods 1, 2, and 3 (Lead-In Period Safety Population)
- Period 2 (RW Safety Population).

The following summaries/analyses will be performed:

- An overall summary of AEs including the number and percentage of patients who experienced TEAE, TEAE by maximum severity, death, SAE, TEAE possibly related to study treatment occurring in  $\geq 5\%$  of patients in the total ixekizumab group, SAE judged by investigator as possibly study treatment related (for combined periods only), discontinuations from the treatment due to an AE, and TEAEs of special interest.
- TEAE by SOC and PT.
- TEAE by maximum severity, SOC, and PT.

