The overall summary of AEs will also be provided for the RW Safety Population during Period 3, Long-Term Ixekizumab Treatment Efficacy Population and Ixekizumab Structure Population by treatment groups.

Follow-up emergent adverse events will be summarized for the Follow-Up Period Population for Period 4:

- FEAEE by PT.

In general, for all AE-related summaries, the number and percentage of patients experiencing the events will be presented by treatment group. In general, events will be ordered by decreasing frequency in the Combined Ixekizumab group, followed in the order of ixekizumab Q2W, ixekizumab Q4W, and placebo (when applicable) group, within SOC and/or PT for sorting.

A by-patient listing of all AEs will be provided.

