### **6.13.3. Deaths, Other Serious Adverse Events, and Other Notable Adverse Events**

By-patient listings of deaths, SAEs, and AEs leading to discontinuation will be provided, respectively.

All deaths will be included, regardless of the investigator's or the sponsor's judgment about causality, including:

- any deaths occurring during participation in the study in the database for which data are being presented
- any deaths occurring after a patient leaves (is discontinued from or completed) the study in the database for which data are being presented if the death is:
  - the result of a process initiated during the study, regardless of when it actually occurred, or
  - occurs during the Period 4 after discontinuation of study drug.

An SAE is any AE that results in 1 of the following outcomes: death, life-threatening, initial or prolonged hospitalization, disability or permanent damage, congenital anomaly or birth defect, or any other serious/important medical events.

The following summary tables (including treatment group comparison for Period 2) will be provided for the Lead-In Period Safety Population for Combined Periods 1 and 2 and Combined Periods 1, 2, and 3, and RW Safety Population for Period 2:

- SAEs by PT
- AEs that lead to treatment discontinuation (including death) by PT.

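### The overall AE summary counts possibly related TEAEs only if they reach 5% of the total ixekizumab group, so it undercounts them and can distort the Period 2 comparison in either direction

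*SAP*

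**What the plan says.** SAP 6.13.2 lists the contents of the overall AE summary. One item is "TEAE possibly related to study treatment occurring in" at least 5% "of patients in the total ixekizumab group, SAE judged by investigator as possibly study treatment related (for combined periods only"). The cut-off refers to the total ixekizumab group alone. The qualifier about combined periods stands directly after the related-SAE item.

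The same section states that "treatment comparisons between treatment groups in Period 2 will be conducted using a" Fisher's exact test. Table RHBY.6.1 gives the contrasts for the RW Safety Population: "Total IXE vs. Placebo IXE80Q2W vs. Placebo IXE80Q4W vs. Placebo". Protocol 10.3.4 makes that population in Period 2 the basis of the primary safety analyses.

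The other planned AE output is all-causality and has no frequency threshold: "TEAE by SOC and PT" and TEAEs by maximum severity in 6.13.2, SAEs by PT and "AEs that lead to treatment discontinuation (including death) by PT" in 6.13.3, and the special-topic tables in 6.13.3.1. In addition, "A by-patient listing of all AEs will be provided". The 5% row is the only listed table entry that counts TEAEs by the investigator's causality judgement, which protocol 9.2 requires for each AE.

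**The concern.** A row labelled as possibly related TEAEs will be read as the number of patients who had one. With the cut-off it is not that number, because a patient whose related events all fall in terms below 5% is not counted.

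The second problem is the comparison. If the 5% is applied term by term, a term enters the row when its observed ixekizumab count happens to be high enough. The ixekizumab percentage among the selected terms is then biased upward by selection, while the placebo percentage is not. Testing one against the other does not compare like with like. The same rule also removes terms that are real but uncommon on ixekizumab, and terms that are common only on placebo. Period 2 is the only placebo-controlled period, so a false or a concealed difference in this row would matter to the causality-based safety summary.

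**Working it through.** **Inputs.** SAP 5.2: "Approximately 100 patients who achieved a state of sustained remission on IXE80Q4W will be randomized in a 2:1 ratio to IXE80Q4W or placebo", and the same for Q2W, about 200 in total. Hence 200 × 2/3 ≈ 133 on ixekizumab and 200 × 1/3 ≈ 67 on placebo. The plan's only related figure is the power statement for flare (over 99%, 10% v 70%, two-sided Fisher). Exact enumeration at 133 v 67 gives more than 99.99%, so that statement reproduces; here it supplies only the arm sizes. Rates of possibly related TEAEs are **not in the documents**. All rates below are assumptions, with terms taken as independent.

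**Step 1: what the cut-off means.** 0.05 × 133 = 6.65, so a term needs at least 7 ixekizumab patients (7/133 = 5.3%).

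**Step 2: one term, same true rate in both arms.** The chance of passing is P(X ≥ 7) with X ~ Binomial(133, p). The mean ixekizumab rate given passing is E[X | X ≥ 7]/133. Placebo stays at p.

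| True rate | Passes | Ixekizumab mean if passed | Placebo |
|---|---|---|---|
| 2% | 1.8% | 5.6% | 2% |
| 3% | 10.6% | 5.8% | 3% |
| 4% | 28.4% | 6.1% | 4% |
| 5% | 50.0% | 6.5% | 5% |
| 8% | 91.4% | 8.4% | 8% |
| 10% | 98.3% | 10.1% | 10% |

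The selection effect is marked below about 5% and negligible from about 8% to 10%.

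**Step 3: the whole row, no true difference.** Simulation of patients with any related TEAE in a term that passes. The unfiltered percentage is 1 − Π(1 − p) over terms; for ten terms at 4% it is 1 − 0.96^10 = 33.5%. The last column is the chance of a two-sided p ≤ 0.05 with ixekizumab higher.

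| Assumed terms | Unfiltered, each arm | Row, ixekizumab v placebo | False result, ixekizumab worse |
|---|---|---|---|
| 20 at 3% | 45.6% | 11.7% v 6.2% | 15.3% |
| 10 at 4% | 33.5% | 16.3% v 10.9% | 11.5% |
| 6 at 4% | 21.7% | 10.1% v 6.6% | 6.1% |
| 10 at 3% | 26.3% | 6.1% v 3.2% | 5.8% |
| 20 at 2% | 33.2% | 1.9% v 0.7% | 1.8% |
| 10%, 6%, and 10 at 2% | 30.9% | 15.2% v 13.9% | 3.0% |
| 10%, and 20 at 1% | 26.4% | 10.0% v 9.8% | 1.4% |
| 20%, and 10 at 0.5% | 23.9% | 20.0% v 20.0% | 1.8% |

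Without the filter, the false result in that direction is about 1.5% to 2%. The artefact thus runs from about 0 to about +5 points (16.3 − 10.9 = 5.4; 11.7 − 6.2 = 5.5). The share of related ixekizumab events left out was 20% with one dominant 20% term, 56% to 79% in intermediate profiles, and 95% or more when all terms were at 1% or 2%.

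**Step 4: a true ixekizumab excess below the cut-off.** Take five terms at 3% v 0.5%. Unfiltered: 1 − 0.97^5 = 14.1% v 1 − 0.995^5 = 2.5%, a difference of 11.6 points. The filtered row shows +2.9 points, and the chance that Fisher flags ixekizumab as worse falls from 78% to 13%. A single term at 3% on ixekizumab and 0% on placebo is dropped 89% of the time; one at 4% v 0.5%, 72%.

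**The case against.** The strongest reply is that the text does not fix the reading. The 5% might be a display rule for the related-TEAE category as a whole; then there is no term-level selection and the figures above do not apply. The combined-periods qualifier might cover both related items; then the row is never compared with placebo, since the Lead-In Period Safety Population has only ixekizumab groups and no inferential statistics. Both are possible. Neither is the natural reading: the qualifier follows the SAE item, and the threshold phrase follows the TEAE. Neither gives a sound row either. On the first, whether the row appears depends on the observed ixekizumab rate. On the second, the combined-period row still undercounts if the 5% is per term, and Period 2 has no relatedness summary.

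Two stronger inferences are tempting and should not be drawn. One is that the row is biased against ixekizumab. Step 3 shows that direction only when many terms lie near 3% to 4%; with common terms it nearly vanishes, and Step 4 shows the opposite. The other is that the plan hides most related events. The omitted share depends wholly on assumed rates, and the events themselves remain in the unthresholded TEAE tables, the special-topic tables and the listing. What is lost is their tabulation as possibly related.

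Nor are SAEs missing from Period 2: SAP 6.13.3 compares all SAEs by PT there. Only a causality sub-count is absent, and relying on all-causality comparison in the controlled period is defensible.

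**Conclusion.** The point stands in limited form. On the natural reading, the only tabulated count of possibly related TEAEs is filtered on one arm's observed data and then compared between arms. It undercounts patients with a related TEAE whenever such events occur in terms below the cut-off, and it can create or conceal a difference. Under the assumed profiles with no true difference, the artefact is about 0 to +5 points against ixekizumab; with a true excess in terms below 5%, most of the signal can be lost. These sizes rest on 133 v 67 patients, independent terms and rates that the documents do not supply, so the actual size and direction cannot be stated. One row of the safety overview is affected. The all-causality TEAE and SAE tables, the listing, the efficacy tests and their error control are not. The change is worth making because the row is misleading as specified and easily corrected.

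**What to change.** In SAP 6.13.2, replace the thresholded row by the number and percentage of patients with one or more TEAEs judged possibly related to study treatment. Apply no frequency threshold, and show it by treatment group for each analysis period including Period 2. With equal true rates this removes the selection artefact: across seven assumed profiles the expected difference was 0 within 0.1 point, and the two-sided Fisher error was 3.9% to 4.2%. If a by-term display of related events is wanted, a 5% cut-off can be kept there, triggered by any arm and without a test.

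Optionally, state which items the combined-periods qualifier covers, or add the related-SAE sub-count in Period 2.

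The cost is SAP wording. The causality data are already collected, and the programming becomes simpler.

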### **6.13.3. Deaths, Other Serious Adverse Events, and Other Notable Adverse Events**

By-patient listings of deaths, SAEs, and AEs leading to discontinuation will be provided, respectively.

All deaths will be included, regardless of the investigator's or the sponsor's judgment about causality, including:

- any deaths occurring during participation in the study in the database for which data are being presented
- any deaths occurring after a patient leaves (is discontinued from or completed) the study in the database for which data are being presented if the death is:
  - the result of a process initiated during the study, regardless of when it actually occurred, or
  - occurs during the Period 4 after discontinuation of study drug.

An SAE is any AE that results in 1 of the following outcomes: death, life-threatening, initial or prolonged hospitalization, disability or permanent damage, congenital anomaly or birth defect, or any other serious/important medical events.

The following summary tables (including treatment group comparison for Period 2) will be provided for the Lead-In Period Safety Population for Combined Periods 1 and 2 and Combined Periods 1, 2, and 3, and RW Safety Population for Period 2:

- SAEs by PT
- AEs that lead to treatment discontinuation (including death) by PT.

#### **6.13.3.1. Special Safety Topics including Adverse Events of Special Interest**

Safety information on special topics including AEs of special interest (AESI) will be presented by treatment group and by analysis period.

Table [RHBY.6.8](#) provides the definitions/derivations and analyses methods (including analyses, summaries and by-patient listings) of special safety topics including AESIs.

Potential AESIs will be identified by a standardized MedDRA query (SMQ) or a Lilly-defined MedDRA PT listing. Preferred terms within an SMQ will be classified as broad and narrow. In the Lilly-defined MedDRA PT listings, Lilly has provided the broad and narrow classification. The Lilly-defined broad terms are for a more sensitive search of potential events of interest and the Lilly-defined narrow terms are for a more specific search. Therefore, the summaries will include the classifications of broad term (same as pooling narrow and broad terms together) and narrow term.

Summaries will be provided for the Lead-In Period Safety Population in the Combined Periods 1 and 2, and Combined Periods 1, 2, and 3, and for RW Safety Population in Period 2. Fisher's exact tests will be used to compare the treatment group for the RW Safety Population during Period 2.

In general, an AESI summary will not be provided for the Follow-Up Period Population during Period 4 except for hepatic laboratory tests.

**Table RHBY.6.8. Definitions and Analyses of Special Safety Topics including Adverse Events of Special Interest**

Special Safety Topic	Definition / Derivation	Analysis / Summary / Listing
Hepatic	
Hepatic AE analysis will include events that are potentially drug-related hepatic disorders by using the Medical Dictionary for Regulatory Activities (MedDRA) PTs contained in any of the following standardized MedDRA query (SMQ) or sub-SMQ as defined in MedDRA:
 
 
• Broad and narrow terms in the Liver related investigations, signs and symptoms (20000008)
 
• Broad and narrow terms in the Cholestasis and jaundice of hepatic origin (20000009)
 
• Broad and narrow terms in the Hepatitis, non-infectious (20000010)
 
• Broad and narrow terms in the Hepatic failure, fibrosis and cirrhosis and other liver damage (20000013)
 
• Narrow terms in the Liver-related coagulation and bleeding disturbances (20000015)
 
 
Elevations in hepatic laboratory tests (ALT, AST, ALP, total bilirubin) using Performing Lab Reference Ranges are defined as:
 
 
• The baseline for RW Safety Population during Period 2 is the last non-missing value prior to the first injection in Period 2, and the baseline for the Lead-In Period during the Combined Period 1, 2, and 3 is the last value before the first injection during Period 1, regardless of interruption of ixekizumab treatment.
 
• Include scheduled visits, unscheduled visits, and repeat measurements.
 
• Alanine aminotransferase (ALT) or aspartate aminotransferase (AST): maximum postbaseline measurement <math>\geq 3</math> times (3<math>\times</math>), 5 times (5<math>\times</math>), 10 times (10<math>\times</math>), and 20 times (20<math>\times</math>) the Performing Lab upper limit of normal (ULN) for all patients with a postbaseline value. 
 
◦ The analysis of 3<math>\times</math> ULN will contain 4 subsets: patients whose non-missing maximum baseline value is <math>\leq 1 \times</math> ULN, <math>> 1 \times</math> ULN to <math>< 3 \times</math> ULN, <math>\geq 3 \times</math> ULN, or missing.
 
◦ The analysis of 5<math>\times</math> ULN will contain 5 subsets: patients whose non-missing maximum baseline value is <math>\leq 1 \times</math> ULN, <math>> 1 \times</math> ULN to <math>< 3 \times</math> ULN, <math>\geq 3 \times</math> ULN to <math>< 5 \times</math> ULN, <math>\geq 5 \times</math> ULN, or missing.
 
◦ The analysis of 10<math>\times</math> ULN will contain 6 subsets: patients whose non-missing maximum baseline value is <math>\leq 1 \times</math> ULN, <math>> 1 \times</math> ULN to <math>< 3 \times</math> ULN, <math>\geq 3 \times</math> ULN to <math>< 5 \times</math> ULN, <math>\geq 5 \times</math> ULN to <math>< 10 \times</math> ULN, <math>\geq 10 \times</math> ULN, or missing.
 
◦ The analysis of 20<math>\times</math> ULN will contain 7 subsets: patients whose non-missing maximum baseline value is <math>\leq 1 \times</math> ULN, <math>> 1 \times</math> ULN to <math>< 3 \times</math> ULN, <math>\geq 3 \times</math> ULN to <math>< 5 \times</math> ULN, <math>\geq 5 \times</math> ULN to <math>< 10 \times</math> ULN, <math>\geq 10 \times</math> ULN to <math>< 20 \times</math> ULN, <math>\geq 20 \times</math> ULN, or missing.
 
 
 
• Total bilirubin: maximum postbaseline measurement <math>\geq 1.5</math> times (1.5<math>\times</math>), and <math>\geq 2</math> times (2<math>\times</math>) the Performing Lab ULN for all patients with a postbaseline value 
 
◦ The analysis of 1.5<math>\times</math> ULN will contain 4 subsets: patients whose non-missing maximum baseline
 
 
 
	
Period 2 (Fisher's exact test), Combined Periods 1 and 2, and Combined Periods 1, 2, and 3 (Summary): TEAE by PT within SMQ or sub-SMQ
 
Listing (in Spotfire): TEAE
 
Period 2 (Fisher's exact test), Combined Periods 1 and 2, Combined Periods 1, 2, and 3 and Period 4 (Summary): Elevations in hepatic laboratory tests: maximum baseline category to abnormal maximum postbaseline category


Special Safety Topic	Definition / Derivation	Analysis / Summary / Listing
	
value is <math>\leq 1 \times</math> ULN, <math>> 1 \times</math> ULN to <math>< 1.5 \times</math> ULN, <math>\geq 1.5 \times</math> ULN, or missing.
 
 
○ The analysis of <math>2 \times</math> ULN will contain 5 subsets: patients whose non-missing maximum baseline value is <math>\leq 1 \times</math> ULN, <math>> 1 \times</math> ULN to <math>< 1.5 \times</math> ULN, <math>\geq 1.5 \times</math> ULN to <math>< 2 \times</math> ULN, <math>\geq 2 \times</math> ULN, or missing.
 
● ALP: maximum postbaseline measurement <math>> 1.5</math> times (1.5<math>\times</math>) the Performing Lab ULN for all patients with a postbaseline value, and divided into 4 subsets: patients whose non-missing maximum baseline value is <math>\leq 1 \times</math> ULN, <math>> 1 \times</math> ULN to <math>\leq 1.5 \times</math> ULN, <math>> 1.5 \times</math> ULN, or missing.
 
	
	
Evaluation of Drug-Induced Serious Hepatotoxicity (eDISH) plot: use maximum ALT measurement and maximum total bilirubin measurement with patients having at least 1 postbaseline ALT and total bilirubin, which contributes 1 point to the plot. The measurements do not need to be taken at the same blood draw.
	Period 2, Combined Periods 1 and 2, and Combined Periods 1, 2, and 3: eDISH plot
Cytopenias	
Cytopenias are defined using the PTs from the following 2 sub-SMQs of the Haematopoietic cytopenias SMQ (20000027) as specified in MedDRA:
 
 
● Broad and narrow terms in the Haematopoietic leukopenia (20000030)
 
● Broad and narrow terms in the Haematopoietic thrombocytopenia (20000031)
 
	Period 2 (Fisher's exact test), Combined Periods 1 and 2, and Combined Periods 1, 2, and 3 (Summary): TEAE by PT within sub-SMQ Listing (in Spotfire): TEAE
Infections	
Infections include events in the Infections and infestations SOC and include all such events: serious infections, opportunistic and potential opportunistic infections, infections that require therapeutic intervention (antibiotics, antivirals, antifungals, etc.).
	Period 2 (Fisher's exact test), Combined Periods 1 and 2, and Combined Periods 1, 2, and 3 (Summary): SAE by PT, AE leading to treatment discontinuation by PT
	
Anti-infective medications are defined in Appendix 5 including antibiotics, antifungals, antivirals, or antiprotozoals.
 
Listing of patients experiencing a TEAE of infections will be provided including the following additional information: anti-infective medications use (if treated) with medication start/end dates, indication for use, and route; minimum postbaseline value within treatment Period 1, Period 2, and Period 3 for leukocytes, platelets, lymphocytes, and absolute neutrophils.
	Listing (in Spotfire): TEAE with anti-infective medications.

Special Safety Topic	Definition / Derivation	Analysis / Summary / Listing
	
The list of MedDRA terms used to identify infections that are typically considered to be OIs are found in Appendix 9. This list contains PTs as contained within categories and specific PTs from the Infections and Infestations SOC and the Investigations SOC which can assist in identifying patients of interest. The narrow terms are considered OIs.
 
Listing of patients experiencing a TEAE of OIs will be provided including the following additional information: source of identification (CRF or Lilly specified list), primary/secondary site of infection, primary/secondary infection type, primary/secondary identified by a laboratory diagnostic test (Yes/No), acquired in a Health care setting (Yes/No).
	
Period 2, Combined Periods 1 and 2, and Combined Periods 1, 2, and 3 (Summary):          TEAE of OIs by PT          TEAE of OIs by maximum severity by PT
 
Listing:          TEAE of OIs

Allergic Reactions/Hypersensitivities	
Allergic reactions/hypersensitivity events will be categorized as either potential anaphylaxis or non-anaphylaxis events and summarized separately. Medical review will determine the final categorization of these events.
 
Allergic Reactions/Hypersensitivity Events, Anaphylaxis: Anaphylaxis has been broadly defined as “a serious allergic reaction that is rapid in onset and may cause death” (Sampson et al. 2006). Identification of cases of potential anaphylaxis from the clinical trial data involves two criteria:
 
 
1) designed to specifically identify cases (following Criterion 1) based on narrow terms from the MedDRA SMQ for anaphylactic reaction (20000021). Criterion 1 for anaphylaxis is defined by the presence of a TEAE based on the following MedDRA PTs from the anaphylactic reaction SMQ:           
 
• Anaphylactic reaction
 
• Anaphylactic shock
 
• Anaphylactoid reaction
 
• Anaphylactoid shock
 
• Kounis Syndrome
 
• Type 1 hypersensitivity
 
 
 
2) to identify possible cases, following Criterion 2 as defined by Sampson et al. (2006). Criterion 2 for anaphylaxis requires having TEAEs from two or more of four categories of AEs as described by Sampson et al. (2006). Occurrence of these events should be nearly coincident; based on recording of events on CRFs. All qualifying event must be within 1 day of study drug injection.
 
 
The 4 categories to be considered in Criterion 2 are:
 
 
• Category A: Involvement of the skin-mucosal tissue
 
• Category B: Respiratory compromise
 
• Category C: Reduced blood pressure or associated symptoms
 
• Category D: Persistent gastrointestinal symptoms
 
	
Period 2 (Fisher's exact test), Combined Periods 1 and 2, and Combined Periods 1, 2, and 3 (Summary):          TEAE by maximum severity by PT within Category,          SAE by PT within Category,          AE leading to treatment discontinuation by PT within Category.

Special Safety Topic	Definition / Derivation	Analysis / Summary / Listing
	
The specific MedDRA PTs covered by each of these Criterion 2 categories are shown in Appendix 6. Summaries of Criterion 2 anaphylactic TEAEs will be provided by the specific combination of categories as follows:
 
 
• AB: events based on meeting Category A and Category B (but no other category)
 
• AC: events based on meeting Category A and Category C (but no other category)
 
• AD: events based on meeting Category A and Category D (but no other category)
 
• BC: events based on meeting Category B and Category C (but no other category)
 
• BD: events based on meeting Category B and Category D (but no other category)
 
• CD: events based on meeting Category C and Category D (but no other category)
 
• ABC: events based on meeting Category A, Category B and Category C (but no other category)
 
• ABD: events based on meeting Category A, Category B and Category D (but no other category)
 
• ACD: events based on meeting Category A, Category C and Category D (but no other category)
 
• BCD: events based on meeting Category B, Category C and Category D (but no other category)
 
• ABCD: events based on meeting each of the 4 Criterion 2 categories.
 
 
Summaries of treatment-emergent anaphylactic AEs will be provided for patients meeting each of the 2 criteria and for patients who meet either criteria overall. Severity of treatment-emergent Criterion 2 anaphylactic AEs will be based on the maximum severity of the specific events met by the patient. Maximum severity of an (or overall) treatment-emergent anaphylactic AE will be based on the maximum severity within Criterion 1 and/or Criterion 2.
 
Allergic Reactions/Hypersensitivity Events, Non-Anaphylaxis: TEAEs of allergic reaction/hypersensitivity categorized as non-anaphylaxis events are defined by the narrow terms within Hypersensitivity SMQ (20000214) excluding the PTs noted in Appendix 7 and excluding the anaphylactic events as defined above.
	
	
A by-patient listing will be provided for all patients experiencing TEAE of allergic reactions/hypersensitivities at any time, including status/criterion of anaphylaxis or non-anaphylaxis, and the associated information collected on Allergic / Hypersensitivity Reaction Follow-Up eCRF page if identified by the investigator.
	
Listing (in Spotfire): TEAE including information collected on Allergic / Hypersensitivity Reaction Follow-Up eCRF page

Injection Site Reactions	
Injection site reaction is defined using the PTs from the MedDRA high-level term (HLT) of Injection site reactions as specified by MedDRA excluding the following 10 PTs:
 
 
1) Embolia cutis medicamentosa
 
2) Injection site joint discomfort
 
3) Injection site joint effusion
 
	
Period 2 (Fisher's exact test) Combined Periods 1 and 2, and Combined Periods 1, 2, and 3 (Summary): TEAE by maximum severity by

Special Safety Topic	Definition / Derivation	Analysis / Summary / Listing
	
4) Injection site joint erythema  5) Injection site joint infection  6) Injection site joint inflammation  7) Injection site joint movement impairment  8) Injection site joint pain  9) Injection site joint swelling  10) Injection site joint warmth.
 
The Injection Site Reaction eCRF page captures the injection site reactions identified by the investigator. These TEAEs will be summarized within the MedDRA HLT by maximum severity or category. If more than 1 TEAE of injection site reaction occurs, the event with the worst value (within the individual categories: redness, swelling and pain) will be used.
 
Redness (Scored 0-4)
 
 
[0] Subject's normal skin color, no increased redness
 
[1] Noticeable, but very mild redness
 
[2] Clearly red
 
[3] Bright red
 
[4] Dark with some scar formation
 
 
Swelling (Scored 0-4 after running a finger over injected area)
 
 
[0] No bump
 
[1] Barely noticeable
 
[2] Clear bump but very thin
 
[3] Clear bump 1 mm thick
 
[4] Clear bump 2 mm thick or more
 
 
Pain (including burning) (Scored 0-3)
 
 
[0] None
 
[1] Mild
 
[2] Moderate
 
[3] Severe
 
	
PT within HLT,  SAE by PT within HLT,  AE leading to treatment discontinuation by PT within HLT
 
TEAE identified by the investigator within HLT:  by PT and maximum severity
 
Listing (in Spotfire):  TEAE including information collected on Injection Site Reaction eCRF page

Cerebro-cardiovascular Events	Cerebro-cardiovascular events will be externally adjudicated by the Central Events Committee (CEC) at the Cleveland Clinic, as outlined in the Manual of Operations. The CEC will adjudicate investigator-reported events selected for adjudication and render an assessment as to whether the event represents a confirmed event (meeting the event definition with all necessary documentation), a non-event (does not meet the event definition and likely represents an alternative or nonevent diagnosis), or lacks sufficient	
Period 2 (Fisher's exact test), Combined Periods 1 and 2, and Combined Periods 1, 2, and 3 (Summary):  TEAE by PT within Subcategory

Special Safety Topic	Definition / Derivation	Analysis / Summary / Listing
	
documentation for confirmation of an event. All events which qualify for CEC adjudication will be used for the analysis of cerebro-cardiovascular events. The categories and subcategories of adjudicated events used for the analysis will include the following:
 
 
Cardiovascular 
 
○ Death (Cardiovascular)
 
○ Cardiac Ischemic Event: Myocardial Infarction and Hospitalization for Unstable Angina
 
○ Serious Arrhythmia
 
○ Hospitalization for Heart Failure
 
○ Hospitalization for Hypertension
 
○ Resuscitated Sudden Death
 
○ Cardiogenic Shock
 
○ Coronary Revascularization
 
 
 
● Neurologic 
 
○ Cerebrovascular Event: Transient Ischemic Attack or Stroke (Hemorrhagic, Ischemic and Undetermined)
 
 
 
● Peripheral Vascular Events 
 
○ Peripheral Arterial Event
 
○ Peripheral Revascularization
 
 
 
 
Events will be analyzed using MedDRA PT nested within the CEC assessment (confirmed event, no event, or insufficient documentation for event determination) and the subcategory. Subtypes of stroke (Hemorrhagic Stroke, Ischemic Stroke, and Undetermined Stroke Type) will be displayed in the analyses nested within Cerebrovascular Event. Subtypes of Serious Arrhythmia (Atrial Arrhythmia, Ventricular Arrhythmia, Heart Block, Other, Unknown) will be displayed nested within Serious Arrhythmia.
	
Listing (in Spotfire): TEAE

Major Adverse Cerebro-Cardiovascular Events (MACE)	
MACE (requiring adjudication as defined above) is defined as:
 
 
● Vascular Death (including cardiovascular and cerebro-vascular causes excluding hemorrhagic deaths outside of the central nervous system)
 
● Non-fatal myocardial infarction
 
● Non-fatal stroke (subtypes: hemorrhagic stroke, ischemic stroke, undetermined stroke type)
 
 
Where,
 
 
● Vascular death should be captured as an Event on Adjudication - Death eCRF page with Adjudication Death Type = "Cardiovascular."
 
● Non-fatal myocardial infarction should be captured as an Event on Adjudication - Cardiac Ischemic Event eCRF page with Type of Ischemic Event = "Myocardial Infarction" and the Event is NOT on
 
	
Period 2 (Fisher's exact test), Combined Periods 1 and 2, Combined Periods 1, 2, and 3 (Summary): TEAE by maximum severity by PT within category
 
Listing (in Spotfire): TEAE

Special Safety Topic	Definition / Derivation	Analysis / Summary / Listing
	
Adjudication - Death eCRF page.
 
 
Non-fatal strokes (ischemic, hemorrhagic) should be captured as an Event on Adjudication - Cerebrovascular Event eCRF page with Stroke Cerebrovascular Event Subtype in 1 of the following categories: hemorrhagic stroke, ischemic stroke, undetermined stroke type, and the Event is NOT on Adjudication - Death eCRF page. Subcategories of non-fatal stroke (Hemorrhagic Stroke, Ischemic Stroke, and Undetermined Stroke Type) will be displayed nested within non-fatal stroke category.
 
	
Malignancies	
Malignancy is defined using PTs from the Malignant or unspecified tumors SMQ as specified in MedDRA (SMQ: 20000091, which includes the sub-SMQs: 20000195 [Tumours of unspecified malignancy] and 20000194 [Malignant tumours]). Events will be summarize by the following categories:
 
 
Nonmelanoma Skin Cancer (NMSC) 
 
Basal Cell Carcinoma, PTs include: 
 
Basal cell carcinoma
 
Basosquamous carcinoma
 
Basosquamous carcinoma of skin
 
 
 
Squamous Cell Carcinoma, PTs include: 
 
Squamous cell carcinoma of skin
 
Bowen's disease
 
Lip squamous cell carcinoma
 
Skin squamous cell carcinoma metastatic
 
Keratoacanthoma
 
 
 
 
 
Malignancies excluding NMSC: all PTs in the Malignant or unspecified tumors SMQ excluding the 8 defined NMSC PTs.
 
	
Period 2 (Fisher's exact test), Combined Periods 1 and 2, and Combined Periods 1, 2, and 3 (Summary) : TEAE by PT within category
 
Listing (in Spotfire): TEAE

Depression	Depression is defined using the PTs from the Depression and suicide/self-injury SMQ as specified in MedDRA (SMQ: 20000035, which includes the sub-SMQs: 20000037 [Suicide/self-injury] and 20000167 [Depression (excl suicide and self-injury)]).	
Period 2 (Fisher's exact test), Combined Periods 1 and 2, and Combined Periods 1, 2, and 3 (Summary): TEAE by PT within SMQ and sub-SMQ
 
Listing (in Spotfire): TEAE

Inflammatory Bowel Disease (IBD)	IBD will be identified using the following subcategory and MedDRA PTs. The narrow terms are considered IBD. IBD (Narrow terms)	
Period 2 (Fisher's exact test), Combined Periods 1 and 2, and Combined Periods 1, 2,

Special Safety Topic	Definition / Derivation	Analysis / Summary / Listing
	
 
• Inflammatory Bowel Disease: Inflammatory bowel disease
 
• Crohn's Disease: Crohn's disease
 
• Ulcerative Colitis: Acute haemorrhagic ulcerative colitis; Colitis ulcerative; Proctitis ulcerative
 
 
Non-Specific Terms (Events That Can Occur with IBD (Broad Terms)): The PTs in this category are listed in Appendix 8.
 
Adjudicated IBD will also be reported.
	
and 3 (Summary): TEAE by PT within subcategory.
 
Listing (in Spotfire): TEAE

Interstitial Lung Disease (ILD)	
Potential ILD is defined using the following terms:
 
 
• Broad and narrow terms in the Interstitial lung disease SMQ (20000042)
 
• Additional 6 PTs from Eosinophilic pneumonia SMQ (20000157): 
 
◦ Angiolympoid hyperplasia with eosinophilia (Narrow)
 
◦ Eosinophilic bronchitis (Narrow)
 
◦ Hypereosinophilic syndrome (Narrow)
 
◦ Loeffler's syndrome (Narrow)
 
◦ Pulmonary eosinophilia (Narrow)
 
◦ Pulmonary vasculitis (Narrow)
 
 
 
	
Listing (in Spotfire): TEAE

Abbreviations: AE = adverse event; ALP = alkaline phosphatase; ALT = alanine aminotransferase; AST = aspartate aminotransferase; eCRF = electronic case report form; FEAEE = follow-up emergent adverse event; PT = preferred term; SAE = serious adverse event; TB = tuberculosis; TEAE = treatment emergent adverse event.

